Statistic analysis	For the evaluation of the primary endpoint patients will be dichotomized by the presence or absence of the sealant reinforcement. Further, patients will be categorized by the type of pancreatic fistula rate defined according to the International Study Group of Pancreatic Fistula (ISGPF). Next, a contingency table will be created to calculate positive predictive value, specificity, sensitivity, and c-index. Association between sealant reinforcement and POPF rate will be expressed as odds ratio calculated by logistic regression models with the appropriate covariates. The strength of association between categorical variables will be tested with a chi-square test with Yate's correction. Secondary end points will be analyzed descriptively by tabulation. Chi-square tests will be used to test associations among categorical variables, while Student's t-test or Mann-Whitney U-test will be used to compare continuous normal or non-normal data, respectively. Time dependent variables will be tested by Kaplan-Meier analysis and Cox regression. Statistical analysis will be performed with R.
Sample size	64 patients, 32 in each group
Ethical approval	This study is approved by the Clinical Research Ethics Committee of Aragon (CEICA)
Duration of the study	The study will begin on February 1, 2018. It is estimated a duration of 1.5 years, according to the PD rate of our center (40-50 year). Estimated end date: July 31, 2019.
Participating centers	Division of Hepato-Pancreato-Biliary Surgery, Department of Surgery, Miguel Servet University Hospital

2. PATIENT VISIT AND EVALUATION.

There will be a first visit in an outpatient clinic where the patient will be informed about the study in detail and will be offered to participate in it as long as it meets the selection criteria. Two copies of the informed consent will be signed, one of them for the patient and the other will be kept together with the study documentation. A first evaluation of the patient will be carried out as it appears in the data collection notebook.

3. STRUCTURE OF THE ORGANIZATION.

3.1. Sponsor.

Investigator Initiated Research Grant from Baxter S.L., Chicago, Illinois, United States, convened on March 24, 2017.

3.2. Principal investigators.

Principal investigator:

[name], FACS
Associate Professor at University of Zaragoza
Attending Surgeon in General Surgery
Division of Hepato-Pancreato-Biliary Surgery
Miguel Servet University Hospital
[name]

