Results. Postoperative complication rates were (with NHS-PEG patch/without NHS-PEG patch): pancreatic fistula (A: 7.7%/7.7%; B: 0%/7.7%; C: 0%/15.5%); biliary fistula: 7.7%/15.4%; DGE: 7.7%/7.7%; hemorrhage: 7.7%/15.5%; exitus: 0%/7.7%; readmission: 7.7%/46%; mean stay: 21.3/26.1 days; other complications: 61.5%/46.2%.

Discussion. Sealing with NHS-PEG patch to prevent postoperative pancreatic fistula after DTM pancreaticojejunostomy can offer a new possibility to decrease POPF, with less fistula rate B and C, less hospital stay an less healthcare costs. Randomized controlled trials with larger number of patients should be performed to support this theory.

Therefore, we have design the following randomized controlled trial in order to validate our positive experience with Hemopatch in PD.

5. HYPOTHESIS / OBJECTIVE.

This unicentric, double-blind, randomized study investigates the efficacy and tolerance of Hemopatch in the prevention of POPF type B and C after a PD. The goal for Hemopatch is to reduce the risk of POPF type B and C from 30% to 15%.

6. STUDY DESIGN.

6.1. Type of study.

Unicentric, randomized, controlled, double-blind, prospective study with a parallel design of two groups. After giving informed consent, patients will not know to which group they have been assigned (reinforcement with Hemopatch or not). After the last follow-up visit on postoperative day 30, the patients can receive this information if they wish.

This study is also blind on the part of the observer; the final result will be determined by an independent observer, making this a double-blind study.

6.2. Primary objective and secondary objectives.

Primary endpoint: POPF type B and C, according to the definition of the ISGPF (Bassi, Surgery 2005), that is, the secretion of pancreatic fluid externalized through a drain or removed during a reoperation, independently of the color and / or appearance on day 3 or later, whose amylase is 3 times the values of serum amylase or collections (infected or not) detected by fistulography or other imaging techniques (computed tomography, ultrasound, magnetic resonance imaging). See attached table.

Grade	A	B	C
Clinical conditions	Well	Often well	Ill appearing / bad
Specific treatment*	No	Yes / no	Yes
US / CT (if obtained)	Negative	Negative / positive	Positive
Persistent drainage (after 3 weeks)**	No	Usually yes	Yes
Reoperation	No	No	Yes
Death related to POPF	No	No	Possibly yes
Signs of infections	No	Yes	Yes
Sepsis	No	No	Yes

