- The investigator suspects a serious threat to the patient's well-being. Adverse events (any sign or symptom that affects the patient's well-being) and serious adverse events (life-threatening, prolongs hospital stay, results in persistent disability or leads to death during the observation period), as cardiopulmonary problems, in the gastrointestinal tract, anaphylactic shock or embolism will be recorded through daily postoperative visits until discharge and during the final visit on the 30th postoperative day. All adverse effects of clinical relevance and all serious adverse effects will be recorded in the case report form along with the degree of the complication (according to the Clavien-Dindo classification). The principal investigator must be informed within 24 hours about the serious adverse effects that occur during the hospital stay. The presence of a causal relationship between adverse effect or serious adverse effect and the intervention of the trial will be judged by the investigator. Serious adverse effects will be reported immediately (ie, within 5 days after recognition) by all investigators to the coordinating investigator. The coordinating researcher must inform the responsible ethics committee and the research sponsor. A list of all serious adverse effects must be compiled.

8. DATA.

8.1. Calculation of the sample size.

The sample size was calculated by comparing two proportions, with a level of statistical significance of 5% (alpha) and a statistical power of 80% (1-beta), and taking into account the preliminary data obtained regarding the rate of POPF in the two groups: 23% for the control group, and 7% for the Hemopatch group.

With these assumptions, it will take 57 patients to detect, with an 80% probability and a level of significance of 5%, a decrease of the POPF rate of 23% in the control group to 7% in the experimental group (Hemopatch). Considering an expected proportion of losses of 10%, the sample size will be 64 patients.

8.2. Randomization and groups.

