All study personnel must sign a confidentiality agreement that covers all aspects of the study and its data. The study directors will take particular responsibility for the security of the data, the documents of origin and the information about the patients.

The coordinator of the main study is also responsible for continuing education in Good Clinical Practices (GCP) in accordance with the Declaration of Helsinki.

8.5. Statistical methods and data analysis.

For the evaluation of the primary objective, patients will be dichotomized by the presence or absence of the sealant reinforcement. In addition, patients will be classified by the type of pancreatic fistula defined according to the ISGPF. Next, a contingency table will be created to calculate the positive predictive value, specificity, sensitivity and the c-index. The association between sealant reinforcement and pancreatic fistula rate will be expressed as an odds ratio calculated by logistic regression models with the appropriate covariates. The strength of association between the categorical variables will be tested with a chi-square test with the Yate correction.

Secondary objectives will be analyzed descriptively by tabulation. Chi-square tests will be used to test associations between categorical variables, while Student's t-test or Mann-Whitney U-test will be used to compare normal or non-normal data, respectively. Time-dependent variables will be tested by Kaplan-Meier analysis and Cox regression. The statistical analysis will be carried out with R.

9. PATIENT SAFETY.

A monitoring team will receive all patient data electronically including expected and unexpected events and side effects for all patients in the study. All patient data are analyzed to detect any unusual pattern. There will be permanent contact with the main coordinator of the study and will meet face to face three times a year to evaluate the course of the study based on the data collected.

10. IMPACT ON CLINICAL PRACTICE.

Hemopatch is expected to reduce the risk of postoperative type B and C pancreatic fistula from 30% to 15%, so that the number of patients currently requiring readmission with possible surgeries and interventional radiological procedures is halved. This implies not only clinical but also economic advantages, since a pancreatic fistula can double the cost of hospital treatment.

11. ETHICS AND LEGAL REQUIREMENTS.

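### The primary odds ratio comes from logistic regression with open-ended covariates on about 10 expected events, with no small-sample method and no rule for an arm without events

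*Combined protocol and SAP*

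**What the plan says.** The primary endpoint is binary: "Primary endpoint: POPF type B and C, according to the definition of the ISGPF". Section 8.5 says the association between the sealant and fistula will be "expressed as an odds ratio calculated by logistic regression models with the appropriate covariates"; the synopsis repeats this ("will be expressed as odds ratio calculated by logistic regression models with the appropriate covariates"). The next sentence in each place adds a chi-square test with Yates correction. Neither place says which covariates, or how many, enter the model. Neither gives a method for the odds ratio's confidence interval, says what is reported if an arm has no events, or says whether the chi-square test or the regression coefficient decides the primary question.

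Section 8.1 sizes the trial on "23% for the control group, and 7% for the Hemopatch group", "with a level of statistical significance of 5% (alpha) and a statistical power of 80% (1-beta"), giving 57 patients, raised to 64 (32 per arm) for 10% losses. Section 5 gives a different target: "The goal for Hemopatch is to reduce the risk of POPF type B and C from 30% to 15" per cent. The centre's own case series in the background, 13 patients with the patch and 13 without, reports "pancreatic fistula (A: 7.7%/7.7%; B: 0%/7.7%; C: 0%/15.5" per cent, patch first. That is no B/C fistula with the patch and about 3 of 13 without.

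**The concern.** Logistic regression without further qualification, run in R, is normally read as maximum likelihood with Wald output. That is an inference, since the plan names neither. Such a fit needs events in both arms to give a finite log odds ratio, and it needs a fair number of events per covariate to give one close to the truth. The plan's own rates promise about 10 events in all, and the phrase about covariates is open-ended. Section 7.1 lists age, male sex, obesity, long operation time, soft pancreas and multivisceral resection as risk factors. Only the last is removed by the exclusion criteria, so a model with several adjusters would be consistent with the text.

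Two things are at stake. If no Hemopatch patient has a B/C fistula, the report could show a significant chi-square result beside an odds ratio of 0 with a Wald p-value near 1, and the remedy would be chosen after seeing the data. If several covariates are used, the published odds ratio may be too far from 1.

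**Working it through.** **Plan's own figure.** Two-sided 5%, 80% power, 23% against 7%, pooled formula: n per arm = [1.96·√(2·0.15·0.85) + 0.842·√(0.23·0.77 + 0.07·0.93)]² / 0.16² = (0.990 + 0.414)² / 0.0256 ≈ 77, or 154 in total. The stated 57 does not reproduce as a total. The loss step does: 57/0.9 = 63.3, so 64. I take 32 per arm as planned, and 29 per arm after losses (32 × 0.9 = 28.8).

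**Expected events, n(p₁ + p₂).**
- 23%/7%: 32 × 0.30 = 9.6; 29 × 0.30 = 8.7.
- 30%/15%: 32 × 0.45 = 14.4; 29 × 0.45 = 13.1.

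**Chance of no Hemopatch event, (1 − p)ⁿ.**
- At 7%: 0.93³² = 9.8%; 0.93²⁹ = 12.2%.
- At 15%: 0.85³² = 0.6%; 0.85²⁹ = 0.9%.

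**Worked case: 0/32 with Hemopatch, 7/32 without.**
- Maximum likelihood: odds ratio 0; the fitted log odds ratio keeps falling, with a standard error above 500,000 and Wald p about 1.0.
- Yates: 64·(7·32 − 32)² / (32·32·7·57) = 5.77, p = 0.016. Fisher: p = 0.011.
- Ordinary unadjusted model with a profile-likelihood interval: 0 to 0.26, likelihood-ratio p = 0.001. Exact conditional interval: 0 to 0.61.
- Firth (with arm only, this adds 0.5 to each cell): (0.5/32.5)/(7.5/25.5) = 0.052, profile penalised-likelihood interval 0.0004 to 0.46, p = 0.004.

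**Exact power and type I error.** All 2×2 tables enumerated, 32 per arm, no covariates; a non-estimable Wald result counts as no rejection.

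| | Wald | Yates | Likelihood ratio | Firth profile |
|---|---|---|---|---|
| 23% vs 7% | 28.2% | 29.5% | 45.9% | 41.9% |
| 30% vs 15% | 26.8% | 20.3% | 30.5% | 28.5% |

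Firth type I error is 4.3% at a common rate of 15% and 4.5% at 23%.

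**Effect of covariates.** Simulation, 4,000 trials per setting, 23% vs 7%, 32 per arm. The plan names no covariates, so I assume independent standard normal ones, each with log odds ratio 0.7. Entries are geometric-mean odds ratios.

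| Covariates | True | Maximum likelihood, finite fits only | Firth, all trials |
|---|---|---|---|
| 0 | 0.252 | 0.256 | 0.249 |
| 1 | 0.232 | 0.227 | 0.235 |
| 2 | 0.214 | 0.194 | 0.216 |
| 3 | 0.197 | 0.157 | 0.195 |
| 5 | 0.169 | 0.099 | 0.168 |

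Relative to the truth, the maximum-likelihood odds ratio is about 2% low with one covariate (0.227/0.232 = 0.98), 9% low with two (0.194/0.214 = 0.91), 20% low with three (0.157/0.197 = 0.80) and 41% low with five (0.099/0.169 = 0.59). At 30% vs 15% with three covariates it is 0.286 against 0.337, or 15% low.

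The two estimator columns cover different sets of trials. In trials where maximum likelihood is finite, Firth is nearer 1 than the truth (0.298 with no covariate, 0.233 with three). This is partly because the trials with no Hemopatch event have been set aside.

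**The case against.** The strongest reply is that the regression serves only to express the association, while the test the plan names is the Yates chi-square. Several stronger readings then fail.

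- A reader might infer that the model costs the trial power. The documents do not support this: no Wald test is named, and Yates gives 29.5% against 28.2% for Wald. In zero-event trials Yates still rejects about 78% of the time (0.076 of 0.098).
- A reader might infer that no interval could be reported with a zero cell. That is wrong: a profile or exact interval running from 0 to a finite upper limit is available. What stands is that the plan specifies neither.
- A reader might infer that the adjusted odds ratio will overstate the benefit. At 23%/7% the bias is negligible with none or one covariate. It appears at about two or more, and then only under assumed covariate effects, so it is a risk.
- A reader might take the case series as a sign that a zero cell is likely. But 0/13 has a 39% chance at a true 7% (0.93¹³), and its 95% upper limit is about 25%. Higher risks need a true rate below 7%, and the documents plan on no such rate for B/C fistula.

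It is also fair that Firth is one of several sound choices. An unadjusted likelihood-ratio test has slightly more power. However, in simulation at a common 15% its type I error rose to 7.0% with three covariates and 9.5% with five, and its point estimate stays at 0 with a zero cell.

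**Conclusion.** The point holds as a gap in the analysis specification. The only stated measure of the primary effect rests on about 9.6 expected events (8.7 after losses), with unlimited covariates and no small-sample method. At the planning rates, about one trial in ten (9.8 to 12.2%) would give an odds ratio of 0 with uninformative default output. At the 30%-to-15% goal the figure is 0.6 to 0.9%. A valid p-value from the named test would survive in either case. Overstatement of the odds ratio is possible with two or more covariates, about 20% with three.

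This rests on reading unqualified logistic regression as maximum likelihood with Wald output, on 1:1 allocation at the stated rates and, for the bias figures, on the assumed covariate effects. Severity: should fix. The better estimator does not rescue the sample size: at 32 per arm power is about 42% with Firth and 30% with Yates, against the stated 80%. That is a separate issue.

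**What to change.** In Section 8.5 and the synopsis, replace the unqualified logistic regression with Firth penalised-likelihood logistic regression, for example with the R package logistf, and a profile penalised-likelihood 95% interval. Include arm plus at most one baseline covariate, named now and known before randomisation. Report this model whether or not an arm has zero events. State which single test is primary, the Firth profile test or the Yates chi-square, and label the other as supportive, so that two p-values do not compete. If Firth is chosen, its exact power at the planning rates is 41.9% against 29.5% for Yates, with type I error below 5% at the two common rates checked.

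The cost is a few sentences, slight shrinkage of the odds ratio towards 1 and fewer covariates. The change should be made before any outcome is unblinded, so that the choice of method cannot depend on the data.

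### The Yates-corrected chi-square gives up about 7 points of power against a valid exact test at 32 per arm, and no confidence interval is planned for the fall in fistula risk

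*Combined protocol and SAP*

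**What the plan says.** The primary endpoint is binary. Section 6.2 gives it as "Primary endpoint: POPF type B and C, according to the definition of the ISGPF". In section 8.5, the paragraph on the primary objective sets out three things:

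- A 2×2 summary: "a contingency table will be created to calculate the positive predictive value, specificity, sensitivity and the c-index".
- An effect measure, "expressed as an odds ratio calculated by logistic regression models", with covariates that are not listed.
- A test: "The strength of association between the categorical variables will be tested with a chi-square test with the Yate correction". The synopsis repeats it: "tested with a chi-square test with Yate's correction".

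The goal is expressed as absolute risk. Section 5 says "The goal for Hemopatch is to reduce the risk of POPF type B and C from 30% to 15"%, and section 10 repeats these rates. Section 8.1 plans on 23% vs 7%, and section 8.2 allocates 32 patients to each arm. Neither section 8.5 nor the synopsis mentions a confidence interval, a risk difference or a risk ratio.

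**The concern.** There are two weaknesses in how the primary result will be obtained and reported.

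**The test.** In small samples the continuity correction pushes the true error rate well below the nominal 5%. That is a cost with no return if another test also holds 5% and rejects everything that Yates rejects. In a trial of 64 patients, a real effect could then be declared non-significant only because of the test chosen.

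**The estimate.** Sensitivity, specificity, positive predictive value and c-index describe how well a marker classifies patients. Randomised allocation is not a marker, and none of these indices answers whether risk fell from 30% to 15%. The two arm risks can be read from the planned table, but not their imprecision. In a trial this small, a reader could take a non-significant result as no effect, or take a favourable point estimate as showing that the goal was met.

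**Working it through.** **Inputs.** 32 per arm (section 8.2); rates 23% vs 7% (section 8.1) and 30% vs 15% (section 5); alpha 5% (section 8.1), taken as two-sided; 57 evaluable patients before the 10% allowance for losses (section 8.1).

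**The plan's own power figure.** Section 8.1 says "it will take 57 patients to detect, with an 80% probability and a level of significance of 5"%. The usual two-sided pooled formula gives, per arm,

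n = [1.960·√(2·0.15·0.85) + 0.842·√(0.23·0.77 + 0.07·0.93)]² / 0.16² = 77,

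or 154 in total. The 57 is not reproduced as a total. The allowance for losses is: 57/0.90 = 63.3, rounded up to 64. The sample-size error is a separate matter; it is noted here because it puts the trial in the range where the choice of test matters.

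**Size and power by full enumeration.** With x control and y Hemopatch fistulas, all 33 × 33 tables are listed. Each has probability Bin(x; 32, p₁)·Bin(y; 32, p₂). Power is the sum over rejected tables. Size is the largest such sum with p₁ = p₂, searched over a fine grid of the common rate.

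- Yates rejects if N(|ad − bc| − N/2)² / [n₁n₂m(N − m)] ≥ 3.841, where m is the total number of fistulas.
- Boschloo orders tables by the Fisher p-value and takes the largest rejection region whose maximum size is at most 5%.

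| Test, 32/32 | Maximum size | Power 23% vs 7% | Power 30% vs 15% |
|---|---|---|---|
| Yates | 3.3% | 29.5% | 20.3% |
| Fisher | 3.3% | 29.6% | 21.5% |
| Boschloo | 4.7% | 37.0% | 27.3% |
| Uncorrected chi-square | 6.0% | 45.6% | 30.5% |

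The gap between Boschloo and Yates is 7.4 points (36.97 − 29.53) and 7.0 points (27.33 − 20.30). Boschloo rejects 36 tables that Yates does not, counting both directions; Yates rejects none that Boschloo does not. The uncorrected test is ruled out because it exceeds 5%.

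**Control fistulas needed to reject, 32/32:**

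| Hemopatch fistulas | 0 | 1 | 2 | 3 | 4 |
|---|---|---|---|---|---|
| Yates | 6 | 8 | 9 | 11 | 12 |
| Boschloo | 5 | 7 | 9 | 10 | 11 |

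For example, 7 vs 1: ad − bc = 7·31 − 1·25 = 192, so Yates gives 64·(192 − 32)²/(32·32·8·56) = 3.57, p = 0.059. Boschloo gives p = 0.033. In this range the gain is one event. There is none at two Hemopatch fistulas, which has probability 27.6% at a 7% rate.

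**After losses (57 patients):**

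| Control/Hemopatch | Rates | Yates | Fisher | Boschloo |
|---|---|---|---|---|
| 29/28 | 23% vs 7% | 22.7% | 25.4% | 33.1% |
| 28/29 | 23% vs 7% | 27.3% | 33.1% | 40.8% |
| 29/28 | 30% vs 15% | 16.8% | 19.4% | 23.0% |
| 28/29 | 30% vs 15% | 18.8% | 23.6% | 27.4% |

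Boschloo's maximum size here is 4.9%.

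**The missing interval.** Take 7/32 vs 2/32, close to the planning rates. The difference is 0.219 − 0.0625 = 0.156. The Wilson limits are 0.110 to 0.388 and 0.017 to 0.201. Newcombe's limits are:

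- lower: 0.156 − √[(0.219 − 0.110)² + (0.201 − 0.0625)²] = −0.020
- upper: 0.156 + √[(0.388 − 0.219)² + (0.0625 − 0.017)²] = 0.331

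So a fall of 15.6 points has a 95% interval of −2.0 to 33.1. It includes no benefit and also twice the 15-point goal. The risk ratio is 0.29, with a score interval of 0.07 to 1.11. The expected Newcombe width is 35 points at 23%/7% and 39 points at 30%/15%.

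**Ordinary logistic regression.** The chance of no Hemopatch fistula at a 7% rate is 0.93³² = 9.8%, and the usual odds-ratio estimate is then undefined.

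**The case against.** The strongest reply is that a conventional, pre-specified test that holds its level is not an error. Moving from 30% to 37% power, or from 20% to 27%, matters little beside the stated 80%. That is correct as far as it goes: this is an efficiency gain and does not rescue the design. But it needs no extra patients, and Boschloo loses no rejection that Yates would have made.

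Section 8.5 does not formally say which analysis is primary. Its test sentence speaks of categorical variables in general, and the logistic model could also supply a p-value. This stands as an ambiguity. Yates is the only test named in that paragraph, so reading it as the primary test is fair, and the ambiguity is a further reason to name one.

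The size of the gain depends on the final arm sizes. At 32/32 Fisher's test gains almost nothing over Yates. With 28 control and 29 Hemopatch patients it gains 5.8 points at 23%/7% (33.1 − 27.3). Boschloo has more power than both in every split checked.

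A reader who has the counts can compute an interval, so its absence biases nothing. It still leaves the main estimate of the trial's stated goal without a planned measure of precision.

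Finally, Boschloo and a Newcombe interval can disagree: 8/32 vs 2/32 gives Boschloo p = 0.060 with an interval of +0.6 to +36.4 points. At 32/32 the chance that the interval excludes zero while Boschloo does not reject is 4.4% (23%/7%) or 3.0% (30%/15%). With Yates it is 11.9% or 10.0%.

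**Conclusion.** The concern holds on both counts. Assuming a two-sided 5% level, the named test gives up 7.4 points of power at 23% vs 7% and 7.0 points at 30% vs 15% with 32 per arm. At the planning rates, about 1 trial in 13 would be called non-significant although a valid 5% test rejects. With 57 evaluable patients the loss is 10.4 to 13.5 points at 23%/7% and 6.2 to 8.5 points at 30%/15%, depending on which arm has the extra patient. No interval is planned for the risk difference or ratio, which are the quantities that match the stated goal. The change is worth making but is not a matter of validity: Yates does control the error rate, and even the better test has only 37% or 27% power at 32 per arm.

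**What to change.** Amend section 8.5 and the synopsis before any outcome data by arm are seen:

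1. Name Boschloo's unconditional exact test, two-sided 5%, as the single primary test in place of Yates. Fix the software function and the table orientation in advance, because a transposed table can change the p-value. The 8/32 vs 2/32 result (p = 0.060) is a useful check.
2. Replace sensitivity, specificity, positive predictive value and c-index with the two arm risks, the risk difference (Newcombe 95% interval) and the risk ratio (score 95% interval), all by randomised arm. The score interval stays defined with no Hemopatch fistulas: 5 vs 0 gives 0 to 0.73.
3. State that the Boschloo test governs if it and an interval disagree, or use an interval obtained by inverting an unconditional exact test.
4. Keep the logistic odds ratio as supportive, fitted with Firth's penalty, and list its covariates.

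The cost is a few lines of text and no extra patients. The downsides are a test less familiar to surgical readers and the need for the precedence rule. At 32/32, a score risk-ratio interval that excludes 1 while Boschloo does not reject would occur in 8.6% of trials at 23%/7% and 3.2% at 30%/15%. The sample size in section 8.1 needs its own correction.

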Readmission	No	Yes / no	Yes / no

US, Ultrasonography; CT, computed tomographic scan; POPF, postoperative pancreatic fistula.
*Partial (peripheral) or total parenteral nutrition, antibiotics, enteral nutrition, somatostatin analogue and/or minimal invasive drainage.
**With or without a drain in situ

Secondary endpoints:

- 1) Duration of postoperative hospital stay.
- 2) Duration of stay in intensive care unit.
- 3) Measurement of drainage debit.
- 4) Reinterventions including interventional radiology
- 5) Infection of the surgical site and / or dehiscence of the wound; complications in the deep organ space up to 30 days postoperatively.
- 6) Delayed gastric emptying.
- 7) Biliary fistula.
- 8) Postoperative hemorrhage.
- 9) Death, regardless of the cause.

6.3. Duration of the study.

The study will begin on February 1, 2018. Patients will be recruited at Miguel Servet University Hospital from January 1, 2018 to July 31, 2019. All patients randomly assigned will be followed for 30 days after surgery, or during the total stay in case it is longer than 30 days. They will also be evaluated in external consultations in the postoperative period for 3 months. A period of 4-6 months is considered to evaluate the data and the study will entail 2 years in total.

7. PATIENTS.

7.1. Criteria.

Despite improvements in morbidity after pancreatic resection, POPF after PD remains problematic. The incidence varies markedly in the literature, ranging from 0% to 64%, and 35% are clinically relevant. This great variability is attributed in part to the

indication and extension of the resection, as well as to the comorbidities of the patient. Other factors, such as age, male sex, obesity, prolonged operation time and a soft pancreas, as well as multivisceral resections increase the risk of fistula. The sequelae of pancreatic fistula after PD cover a broad spectrum. These patients often require visits to the emergency department, hospital readmissions, percutaneous drainage guided by interventional radiology, prolonged parenteral antibiotic therapy, radiological surveillance and numerous postoperative visits. The complications derived from the fistula double the cost of hospital treatment and dramatically increase the use of health resources.

7.2. Recruitment.

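### Section 8.5 gives no rule for in-hospital deaths in the hospital and ICU stay comparisons, so the planned methods can mis-score them; the size and direction of any bias are unknown

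*Combined protocol and SAP*

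**What the plan says.** Section 6.2 (and the synopsis) lists "Duration of postoperative hospital stay" and "Duration of stay in intensive care unit" as secondary endpoints 1 and 2, and "Death, regardless of the cause" as endpoint 9. Section 8.3 collects both stays as durations. Neither section links death to the stay endpoints.

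On analysis, section 8.5 states that "Secondary objectives will be analyzed descriptively by tabulation". It then adds tests: "Student's t-test or Mann-Whitney U-test will be used to compare normal or non-normal data", and "Time-dependent variables will be tested by Kaplan-Meier analysis and Cox regression". It does not say whether stay is treated as continuous or as time-dependent. For the time-to-event route it names no event, censoring rule or competing event.

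On follow-up, section 6.3 says: "All patients randomly assigned will be followed for 30 days after surgery, or during the total stay in case it is longer than 30 days". A long stay is therefore followed to its end, and in-hospital death is the main reason why a stay would not end in discharge.

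**The concern.** Length of stay has a clear meaning only for patients who leave hospital alive. Each route that section 8.5 allows handles a death badly unless a rule is added:

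- **t-test or Mann-Whitney on raw days.** A death on day 5 enters as a 5-day stay, which is a good result.
- **Kaplan-Meier or Cox with death coded as the end of stay.** The same fault.
- **Kaplan-Meier or Cox with death censored.** The death is no longer a short stay, but the patient is treated as someone who could still be discharged, and the probability of discharge is overstated.

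Deaths cannot be assumed to be balanced. The grading table in section 6.2 allows fistula-related death in grade C, and section 7.6 expects high mortality there. Preventing grade B and C fistula is the purpose of the patch, so an effective patch could change mortality as well as stay. The pilot summary cites shorter stay as a benefit, so the trial's stay result is likely to be cited too. Without a rule, the handling of deaths could be chosen after the data are seen.

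**Working it through.** The plan states no target difference, standard deviation or power for either stay endpoint, so there is no figure of its own to reproduce. The pilot gives nothing on ICU stay, so the sizes below concern hospital stay only.

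**Inputs from the document.** Pilot mean stay 21.3 days with the patch and 26.1 without, a difference of 4.8. Pilot deaths 0% and 7.7%, which is 0/13 and 1/13. Planned 32 per arm (section 8.2).

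**Assumptions not in the document.** Stay is lognormal with a coefficient of variation (CV) of 0.4 or 0.6. Day of death is uniform over a stated range. The pilot means are taken as the stay in the absence of death, although the pilot does not say how its one death was counted.

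**Shift in the mean on raw days.** If a proportion p of the control arm dies, at mean day d, the control mean becomes 26.1 − p × (26.1 − d). With p = 0.077 (0.077 × 32 ≈ 2.5 deaths) and no deaths with the patch:

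- Days 2-20, d = 11: 26.1 − 0.077 × 15.1 = 24.94; difference 24.94 − 21.3 = 3.64 days.
- Days 10-40, d = 25: 26.1 − 0.077 × 1.1 = 26.02; difference 4.72 days.
- Days 15-45, d = 30: 26.1 + 0.077 × 3.9 = 26.40; difference 5.10 days.

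The mean is unchanged when d equals 26.1. Deaths earlier than that on average shrink the difference; later ones enlarge it.

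If both arms have the same proportion of deaths with the same timing, the difference becomes 4.8 × (1 − p). At 3.8% in each arm this is 4.8 × 0.962 = 4.62 days.

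**Mann-Whitney power on raw days (simulation, two-sided 5%, 32 per arm).**

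| Deaths, control vs patch | CV 0.6 | CV 0.4 |
|---|---|---|
| None, or survivors only | about 28% | about 52% |
| 7.7% vs 0%, days 2-20 | 17% | 30% |
| 7.7% vs 0%, days 10-40 | 30-31% | not tabulated |
| 7.7% vs 0%, days 15-45 | 35-37% | not tabulated |
| 3.8% in each arm, days 2-20 | 26-27% | not tabulated |

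The early-death loss is 28 − 17 = 11 points at CV 0.6 and 52 − 30 = 22 points at CV 0.4. In a separate run with exactly two deaths in each arm on days 2-10, power was 41% on raw days and 41% with deaths ranked worst at CV 0.4, and 21% against 20% at CV 0.6. Power is lower than with no deaths, but the choice of rule hardly matters and the mean difference is still about 4.5 days.

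**Censored deaths.** If 7.7% of an arm dies in hospital and all others go home, the true proportion ever discharged alive is 100 − 7.7 = 92.3%. Kaplan-Meier with deaths censored climbs to 100% if the longest stay ends in discharge.

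**The case against.** The case against giving this much weight is good, and most of it stands.

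- **A reader might infer that early deaths will be scored as short stays and that the comparison is biased against the patch.** The document does not support this. Section 8.5 does not say which route applies to stay, and under censoring a death is not a short stay. Nor does any section give the timing of deaths. Grade C fistula is described with sepsis, intensive care, reoperation and drainage beyond three weeks, so deaths from it can follow long stays. The day 10-40 and day 15-45 rows show the bias vanishing and then reversing.
- **A reader might measure the harm by comparing raw days with worst rank** (17% against 44% at CV 0.6; 30% against 69% at CV 0.4). That is not a measure of bias. Worst rank also counts the assumed mortality difference as an effect. The fair comparators are no deaths or survivors only.
- **A reader might infer that the stay result could hide a harmful patch.** Deaths are reported as endpoint 9, and section 7.7 requires a list of serious adverse events, so excess deaths would be visible there.
- **The mortality input is one death.** Exact 95% intervals for 1/13 and 0/13 are 0.2-36% and 0-25%, which is no evidence of a difference between arms.
- **These endpoints are secondary and mainly descriptive.**

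What remains is the missing rule. The separate mortality table shows that deaths occurred, but does not say how they entered the stay comparison.

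**Conclusion.** The gap is real and the bias is conditional. As written, every available route mis-scores in-hospital deaths unless a rule is supplied, and none is. If deaths are early and concentrated in the control arm, raw days would understate a benefit on stay: 4.8 days would appear as about 3.6, with a loss of about 11 to 22 points of power. If deaths fall around the usual length of stay, or are equal in both arms, there is little bias. If they come later, the bias runs the other way.

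These sizes rest on one pilot death in 13, an assumed spread of stay and assumed days of death. They show that the rule can matter, not that it will. The primary fistula comparison is not affected. This is a minor specification point, worth settling before the data are analysed.

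**What to change.** Add a short paragraph to section 8.5 that names one analysis for hospital stay and ICU stay and states how in-hospital death enters it. Either of these would do:

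1. **Time to discharge alive, with death as a competing event.** Patients who die stay in the risk set, undischarged, to the end of a stated window. Report the cumulative incidence of live discharge by arm. Section 6.3 follows stays beyond 30 days to their end, so the window should be set to match.
2. **Mann-Whitney with in-hospital deaths given the worst rank.**

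With either, tabulate in-hospital deaths by arm and stay among survivors alongside. For ICU stay, state the equivalent event (leaving the ICU alive).

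The cost is a few sentences and a few lines of R. No extra patients or visits are needed: section 8.3 collects the stays, and section 7.7 records deaths through daily visits. The downside is that either result combines stay with survival, so it must be read next to the mortality table. Survivors' stay alone is not a full answer, because survivors may differ between arms.
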